Enrollment of a total of approximately 225 subjects is planned. The Bayesian posterior probability that the clinical success rate at the PTE Visit is within 0.10 of that of the nitrofurantoin group will be estimated for each omadacycline dose group. The target probability is 0.80. If the true underlying clinical success rates for the nitrofurantoin and omadacycline dose groups are 0.82, then the sample size of N=50 per treatment has approximately 79% power/probability to yield the target probability (N=53 per treatment for 80% power). The sample size may be increased for a particular omadacycline dosing group by changing the randomization ratio and/or dropping a dose group to achieve improved power / probability of achieving the target probability that clinical success rates for a dose group is within 0.10 of that of the nitrofurantoin group. If required to improve the precision of the interim or projected final analyses estimates of response rates or posterior probabilities, sample size may be increased to a maximum sample size provided in the statistical analysis plan (SAP). Subjects will be randomized (1:1:1:1:1) to five treatment groups.

The following subject analysis populations have been defined:

- Intent-to-treat (ITT): all randomized subjects.
- Safety: all randomized subjects who receive any amount of test article.
- The microbiological ITT (micro-ITT) population will consist of subjects in the ITT population who have a study-qualifying pre-treatment positive Baseline urine culture with 1 or 2 uropathogens at $\geq 10^5$ Colony Forming Units (CFU)/mL. (ME) population will include subjects in the CE population who have a study-qualifying pre-treatment Baseline urine culture with 1 or 2 uropathogens at $\geq 10^5$ CFU/mL.
- The clinically evaluable (CE) population will consist of all ITT subjects who received test article, have a qualifying infection, an assessment of outcome, and meet all other evaluability criteria detailed in the SAP.
- The microbiologically evaluable (ME) population will include subjects in the CE population who have a study-qualifying pre-treatment Baseline urine culture with 1 or 2 uropathogens at $\geq 10^5$ CFU/mL.

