5.1.1 Adaptive Design

This is an adaptive dose-response finding study. Initially, subjects will be randomized (1:1:1:1:1) to five treatment groups. During the course of the study, a Bayesian analysis will be used to adaptively allocate new subjects to one of the treatment arms, conditional on the availability of primary efficacy endpoint data (investigator assessment of clinical response at PTE). When there is sufficient information available about the dose-response, results from the Bayesian analysis will be reviewed by a DMC to determine if enrollment in any

omadacycline treatment arms should be stopped or modified. Modifications to omadacycline dosing regimens/treatment arms may also be based on safety and tolerability.

Bayesian analyses will be conducted after efficacy data (investigator assessment of clinical response at PTE) are available for approximately 40, 80, and 100 subjects in order to:

1. Determine omadacycline dose group(s) that can be dropped from the trial, or
2. Modify the randomization ratios among the dose groups to improve the precision of the selected dose groups comparison of clinical success to that of the nitrofurantoin group.

Additional analyses may be carried out for the same two purposes. Response criteria are targeted toward estimating the probability that the clinical success rate (proportion of subjects) for each omadacycline dose group is within 10% of that of the nitrofurantoin group. If at the analyses, that probability falls below 30% for a particular dose group, recruitment for that dose group may be stopped or curtailed. If that probability exceeds 80% for a particular omadacycline dose group, recruitment for that dose group may be increased to improve the precision of the estimate.

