7.4 Dose Selection Rationale

The dosing regimen of omadacycline selected for this study is based on the nonclinical and clinical experience to date, including in vitro antibacterial activity, PK characteristics, clinical efficacy in prior studies, and the overall safety and tolerability profile. Key considerations in dose selection are summarized below:

- While the driver of efficacy for omadacycline in UTI is not known, a pragmatic assumption was made that maximizing the time of urine concentration above pathogen MIC (ideally, throughout the dosing interval) would be desirable.
- In PTK0796-UUTI-15103, omadacycline dosed as 300 mg po q12h on Day 1 followed by 300 mg po daily for 5 days and 450 mg po q12h on Day 1 followed by 450 mg po daily for 5 days both demonstrated high urinary concentrations on Day 1 and Day 5. For the 300 mg dosing group, over the 24-hour dosing period, mean urinary concentrations ranged from 14 to 20 µg/mL on Day 1 and 17 to 30 µg/mL on Day 5. For the 450 mg dosing group, over the 24-hour dosing period, mean urinary concentrations ranged from 11 to 25 µg/mL on Day 1 and 30 to 48 µg/mL on Day 5.
- In PTK0796-UUTI-15103, both the 300 mg and 450 mg omadacycline treatment groups had nausea reported in 60% of subjects. Vomiting occurred in 40% and 20% of the 300 mg and 450 mg treatment groups, respectively. In the recently completed PTK0796-ABSI-16301 study which compared omadacycline 450 mg po every 24 hours (q24h) for 2 doses followed by 300 mg po q24h for a total of 7 to 14 days to linezolid 600 mg po q12h for a total of 7 to 14 days, nausea and vomiting rates of 30.2% and 16.8% were observed. In both studies, most events of nausea and vomiting occurred early in the treatment associated with the loading doses of omadacycline.
- The effect of a light meal administered approximately 1.5 hours before dosing was evaluated using the free base formulation of omadacycline and resulted in approximately 20% decrease in exposure. In the recently completed study PTK0796-DDI-17106, the effect of a light meal administered approximately 1.5 hours before dosing with the same formulation of omadacycline used in the pivotal Phase 3 studies was evaluated. The results demonstrated an approximately 19% to 25% reduction in exposure when a light meal was administered 1.5 hours before dosing.
- The Sponsor has decided to add an omadacycline treatment group dosed at 450 mg twice daily for 7 days. The rationale for the change includes:

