 - 1) Since the driver of efficacy is unknown and the mean renal excretion of a 300 mg oral dose is 14.4%, a regimen that maximizes the tolerated dose of omadacycline may provide additional information on the dose necessary for

clinical and microbiologic success in uUTI and allow comparison to the daily dosed omadacycline treatment groups.

- 6) The proposed dosing of 450mg twice daily for 7 days will provide approximately 2x or greater the amount of omadacycline that is excreted into the urine compared to the daily omadacycline treatment groups.
- 7) Blinded review of the first 145 subjects reveals good tolerability. Nausea has occurred in approximately 10% of all subjects with only a single subject (0.7%) reporting vomiting. There has been only one treatment discontinuation due to adverse events of nausea and/or vomiting reported. Therefore, even if all cases of nausea and vomiting were in a single omadacycline treatment group, nausea and vomiting appears lower than observed in PTK0796-UUTI-15103 study.
- 8) Dose-limiting transaminase increases were seen in Phase 1 studies at 600mg IV which is higher than the exposure at 450mg PO twice daily.
- 9) Increases in heart rate following omadacycline are C_{max} associated. C_{max} concentrations with the 450mg PO dose (1077 ng/mL) at steady state are approximately one-half the C_{max} concentration with the 100mg IV dose (2120 ng/mL) suggesting that heart rate increases above 12-17 bpm observed with 100-200mg IV doses in healthy patients is unlikely following 450mg twice daily dosing.

Therefore based on the pharmacokinetic, clinical, and safety data, the 450mg twice daily dose will increase urinary concentration, may provide additional clinical and microbiologic benefit while maintaining the safety profile observed with daily dosing.

In order to minimize the effect of food on exposure and to potentially minimize the impact of nausea and vomiting during the omadacycline loading dose, omadacycline will be dosed twice on Day 1 with each dose administered approximately 2 hours following a light meal. In addition, all even numbered doses will also be administered approximately 2 hours following a light meal. Given the urinary concentrations observed in PTK0796-UUTI-15103 and the expected impact of a light meal, urinary concentrations should remain above the typical omadacycline MIC₉₀ of 2 µg/mL for *E.coli*, the most common uropathogen in uncomplicated cystitis.

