12.2 Determination of Sample Size

Enrollment of a total of approximately 225 subjects is planned. The Bayesian posterior probability that the clinical success rate at the PTE Visit is within 0.10 of that of the nitrofurantoin group will be estimated for each omadacycline dose group. The target probability is 0.80. If the true underlying clinical success rates for the nitrofurantoin and omadacycline dose groups are 0.82, then the sample size of $N = 50$ per treatment has approximately 79% power/probability to yield the target probability ($N = 53$ per treatment for 80% power). The sample size may be increased for a particular omadacycline dose group by changing the randomization ratio and/or dropping a dose group to achieve improved power/probability of achieving the target probability that clinical success rates for a dose group is within 0.10 of that of the nitrofurantoin group. If required to improve the precision of the interim or projected final analyses estimates of response rates or posterior probabilities, sample size may be increased to a maximum sample size provided in the SAP.

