3.1 Sample Size Considerations

Enrollment of a total of approximately 225 subjects is planned. The Bayesian posterior probability that the clinical success rate at the PTE Visit is within 0.10 of that of the nitrofurantoin group will be estimated for each omadacycline dose group. The target probability is 0.80. If the true underlying clinical success rates for the nitrofurantoin and omadacycline dose groups are 0.82, then the sample size of $N = 50$ per treatment has approximately 79% power/probability to yield the target probability ($N = 53$ per treatment for 80% power).

The sample size may be increased for a particular omadacycline dose group by changing the randomization ratio and/or dropping a dose group to achieve improved power/probability of achieving the target probability that clinical success rates for a dose group is within 0.10 of that of the nitrofurantoin group. If required to improve the precision of the interim or projected final

analyses estimates of response rates or posterior probabilities, sample size may be increased to a maximum sample size of 300 patients.

The decisions affecting changes of randomization to treatment groups, hence affecting total sample size, will be based on the recommendation of the DMC at interim analyses in an unblinded manner. Statistical details relevant to pre-defined decision rules for the DMC are documented in the DMC SAP⁽¹⁾.

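### The 79%/80% in SAP 3.1 does not reproduce from its stated inputs for any arm, and at 225 subjects with equal allocation the late-added Group 4 gets about 16, not 50

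*SAP*

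**What the plan says.** SAP 3.1 takes true success rates of 0.82 in every arm, a margin of 0.10 and a target posterior probability of 0.80, to be estimated for each omadacycline group. On that basis 50 subjects "per treatment has approximately 79% power/probability to yield the target probability", and 53 give 80%. Protocol 12.2 and the synopsis carry the same statement.

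On total size, Protocol 12.2 says: "Enrollment of a total of approximately 225 subjects is planned". On allocation, Protocol 5.1.1 says: "Initially, subjects will be randomized (1:1:1:1:1) to five treatment groups". SAP 3.2 gives the same ratio.

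Protocol 7.4 records that one arm is new: "The Sponsor has decided to add an omadacycline treatment group dosed at 450 mg twice daily for 7 days". One reason given there is tolerability so far: "Blinded review of the first 145 subjects reveals good tolerability". Those subjects were enrolled before Group 4 existed.

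SAP 3.1 lets an omadacycline arm be enlarged "by changing the randomization ratio and/or dropping a dose group to achieve improved power/probability", and adds that "sample size may be increased to a maximum sample size of 300 patients". The decision rules are placed in a separate DMC SAP. No section gives an expected size or a probability for an arm that opens late.

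**The concern.** A single per-treatment figure, attached to each omadacycline group, reads as applying to all four comparisons with nitrofurantoin. Two things prevent that. The probability does not follow from the inputs printed beside it. The sample size of 50 per arm does not fit the planned total, and the shortfall falls on Group 4, the arm that Amendment 2 added.

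Protocol 3.2 says that the data will help to select regimens for later studies. If Group 4 gives an inconclusive result, the plan offers no advance figure for how likely that was even with equal efficacy. A reader who relies on 79% would overrate how informative the Group 4 comparison was planned to be.

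**Working it through.** **Inputs.** True rates 0.82 and 0.82, margin 0.10, target 0.80, total about 225, cap 300 (SAP 3.1). Posterior quantity P(pOMC − pN > −0.10 | data) with Beta(0.5, 0.5) priors (SAP 7.2). Beta(1, 1) is run as a sensitivity case, because Protocol 12.5.1 says only that the prior is uninformative. At least 145 subjects before Group 4 (Protocol 7.4). Ratio 1:1:1:1:1 afterwards (Protocol 5.1.1, SAP 3.2).

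**Formula.** With a = 0.5 or 1, the posteriors are pOMC ~ Beta(a + y1, a + n1 − y1) and pN ~ Beta(a + y2, a + n2 − y2). The probability of reaching the target is the sum of Bin(y1; n1, 0.82) × Bin(y2; n2, 0.82) over all (y1, y2) whose posterior probability is at least 0.80. It is computed by exact enumeration.

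**Step 1: the plan's own figure.** Results for Beta(0.5, 0.5), then Beta(1, 1):
- 50 v 50: 69.2%, 69.2% (stated: 79%).
- 53 v 53: 69.5%, 71.2% (stated: 80%).
- The normal approximation, Φ(0.10/√[0.82 × 0.18 × (1/n1 + 1/n2)] − 0.842), gives 67.7% and 69.1%. By that method 79% needs about 81 per arm and 80% about 84.
- Reading within 0.10 as two-sided gives only 19% and 24%.
- A threshold of 0.70 gives 79.8-80.9% at 50 and about 81% at 53, which is close. Both documents state 0.80.

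**Step 2: head-count.**
- 5 × 50 = 250 and 5 × 53 = 265, against about 225.
- Group 4, five arms open: (225 − 145)/5 = 16. Each other arm: 145/4 + 16 = 52.25.
- If Group 4 opened after 165 subjects: 60/5 = 12 v 165/4 + 12 ≈ 53. After 185: 40/5 = 8 v 185/4 + 8 ≈ 54.
- At the cap, five arms open: (300 − 145)/5 = 31 v 145/4 + 31 ≈ 67.

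**Step 3: probability at those sizes (target 0.80).**

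| Case | Sizes | Beta(0.5, 0.5) | Beta(1, 1) |
|---|---|---|---|
| Other omadacycline arms at 225 | 52 v 52 | 70.0% | 70.0% |
| Group 4 at 225 | 16 v 52 | 54.0% | 48.8% |
| same, one control more | 16 v 53 | 50.0% | 49.2% |
| same, slightly smaller | 15 v 51 | 51.4% | 45.6% |
| same, slightly larger | 17 v 53 | 52.1% | 49.3% |
| Group 4 opened after 165 | 12 v 53 | 48.3% | 42.8% |
| Group 4 opened after 185 | 8 v 54 | 44.3% | 34.1% |
| Group 4 at 300, five arms open | 31 v 67 | 62.7% | 61.2% |

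At a 0.70 threshold, 15-17 v 51-53 gives about 58-66%, against 81% at 52 v 52.

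**Step 4: permitted adaptation.** Dropped-arm cases share all subjects after the first 145 equally among the arms still open.
- 225, one arm dropped: 80/4 = 20 v 56, 57% (51%).
- 225, two dropped: 80/3 ≈ 27 v 63, 61% (57%).
- 300, one dropped: 155/4 ≈ 39 v 75, 68% (65%).
- 300, two dropped: 155/3 ≈ 52 v 88, 73% (72%).
- 300, five arms open, remaining 155 at an illustrative 2:1:1:1:1 in favour of Group 4: 155 × 2/6 ≈ 52 v 145/4 + 155/6 ≈ 62, about 70%.
- With equal allocation among open arms, Group 4 reaches 50 at a total of 145 + 5 × 50 = 395, 145 + 4 × 50 = 345 or 145 + 3 × 50 = 295. Only the last is under the cap.

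**The case against.** The strongest reply is that this is an adaptive trial and equal allocation is only its starting point. The Amendment 2 summary of changes says that the total was raised to accommodate the new arm, calls 53 per arm the initial goal, and points to DMC changes of ratio or a dropped group as the way to improve power. The 2:1:1:1:1 illustration shows that a modest permitted change can close the gap. A reader might infer that Group 4 will have only 16 subjects, or that the design cannot do better. The documents support neither: 16 is the consequence of no adaptation. What remains is that adaptation is permissive and no Group 4 figure is given. The scheduled looks, at 40, 80 and 100 subjects with data (SAP 3.4), would also rest largely or wholly on subjects enrolled before Group 4. Adaptation informed by Group 4 data would then depend on the optional additional analyses.

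A second reply is that the percentages come from a model that does not return the sponsor's figure. This stands as a limit on their level. The Group 4 result also moves by 4 points when one control is added. It does not remove the shortfall, which appears under both priors and at both thresholds. Nor does non-reproduction prove the sponsor's calculation wrong, since the DMC SAP may define another model.

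A reader might also infer that the stated 79% holds for the three once-daily arms and fails only for Group 4. The calculation does not support that: those arms meet the N of 50, but at 52 v 52 they reach 70%.

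Third, the practical consequence is limited. SAP 7.2 declares non-inferiority from the 95% confidence interval and attaches no 0.80 rule to the final posterior. With 1.96 in place of 0.842 in the normal formula, that test has about 26% power at 52 v 52 and 15% at 16 v 52. Inference is nominal (SAP 5.1.4) and intervals will be reported. This limits the weight of the point; the sample-size statement still needs correcting.

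**Conclusion.** The concern holds in two parts.

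(a) The 79% and 80% are not reproduced for any arm from the inputs given. The exact figures are about 69% and 70-71%, a gap of roughly 10 points. A 0.70 threshold would nearly explain it; so might a different model in the DMC SAP.

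(b) The N basis fails for Group 4 at the planned total unless allocation is adapted: about 16 or fewer subjects against 50, and about 46-54% (15-17 v 51-53) against about 70% for the other arms. At a 0.70 threshold the contrast is 58-66% against 81%.

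The head-count assumes even four-arm allocation before Group 4 opened, no earlier ratio change or dropped arm, all five arms open at equal ratio afterwards, and a total of about 225. Because at least 145 subjects preceded Group 4, 16 is an upper figure under those assumptions. The direction and existence of the shortfall are robust; its level in percentage points depends on the model. The final analyses are not invalidated. The stated justification should be corrected.

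**What to change.** In SAP 3.1, which prevails over the protocol (SAP 1), and in Protocol 12.2 and the synopsis at the next amendment:
1. State the expected N per arm under Amendment 2, from total enrolment when Group 4 opened and the initial planned ratio. This needs no unblinded allocation data.
2. State the probability per arm on those sizes, with Group 4 shown separately.
3. Name the prior, threshold and model behind 79% and 80%, and correct those figures if they do not reproduce.
4. Say that Group 4 reaches the N=50 basis only if the ratio is changed or dose groups are dropped, together with growth toward the cap of 300 where needed.

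Any re-weighting is for the sponsor and DMC to decide.

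The cost is a short recalculation, one enrolment count from the sponsor, and a few sentences in a SAP amendment, which SAP 3.5 allows before database lock. Protocol text can change only by written, approved amendment (Protocol 13.6.2), so it can wait for the next one. No extra patients or visits are needed, and no analysis changes.

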3.2 Randomization and Blinding

Approximately 225 female subjects will be enrolled at up to 25 sites. Subjects will be randomized (1:1:1:1:1) to five treatment groups (see [Table 1](#)).

Table 1 Description of Treatment groups

Group	Test Article	Study Day 1	Study Days 2-7*
1	omadacycline	300 mg po q12h, fed	300 mg po q24h
2	omadacycline	450 mg po q12h, fed	300 mg po q24h
3	omadacycline	450 mg po q12h, fed	450 mg po q24h
4	omadacycline	450 mg po q12h, fed	450 mg po q12h
5	nitrofurantoin	100 mg po q12h, fed	100 mg po q12h

q12h= every 12 hours, q24h= every 24 hours

*Odd doses on Study Days 2-7 should be taken in a fasted state. Even doses on Study Days 2-7 will be administered approximately 2 hours following a light meal

The site delegate will contact the Interactive Response System (IxRS) after confirming that the subject fulfills all the inclusion criteria and none of the exclusion criteria. The IxRS will assign a test article to the subject based on a computer-generated randomization schedule. The randomization will be a blocked randomization sequence and centrally balanced as defined in the IxRS specifications. Subjects randomized into the study will be assigned the treatment corresponding to the next available number from the computer-generated randomization schedule. The subject is considered randomized when the IxRS provides the test article assignment, regardless of whether the subject actually receives any medication. As this is an adaptive design trial, any updates to the randomization schedule based upon the Bayesian analysis will be incorporated into the IxRS system.

3.3 Data Monitoring Committee

A DMC will provide ongoing monitoring of data in an unblinded manner. The charter for the DMC will outline membership, roles, and responsibilities. This will include a detailed description of the manner in which security and blinding of the data for the study blinded management team will be maintained, in addition to the procedures that ensure the independence and objectivity of the DMC's activities. The purpose of DMC is to monitor safety, tolerability, and to provide efficacy decisions based on the Interim Analyses as described in [Section 3.4](#), for further details please refer to DMC Charter.

3.4 Interim Analyses

This is an adaptive dose-response finding study. Bayesian efficacy analyses will be conducted when data is available from 40, 80 and 100 subjects for the DMC to:

- Determine if omadacycline dose group(s) can be dropped from the trial, or
- Modify the randomization ratios among the omadacycline dose groups to improve the precision of the selected dose group comparison of clinical success to that of the nitrofurantoin group.

Detailed description of the analyses and decision rules related to efficacy are included in the DMC SAP.¹

Interim analyses will be performed by an independent unblinded statistician. Results will be reviewed by the DMC in closed session. Of note, modifications to omadacycline dosing regimens/treatment arms may also be based on safety and tolerability. The DMC's decisions will be documented in meeting minutes.

PRA Health Sciences and Sponsor's study teams will remain blinded throughout the course of the study.

3.5 Final Analyses and Reporting

All analyses identified in this SAP will be performed after the end of study as defined in the study protocol.

This SAP and any corresponding amendments will be approved before database lock.

The randomization codes will not be unblinded until this SAP has been approved and issued.

